
#### Assessments.

**Pre-intervention focus group.** Separately, and prior to the enrollment in the intervention, we plan to conduct a small focus group of individuals (N = 8-10) from the Duke Dining Service staff in order to (1) better understand perspectives and experience with physical activity; (2) gauge interest in aspects of the study, and (3) understand format preferences for presenting and collecting information. The goal is to gather information to improve delivery of the intervention to participant stakeholders. Individuals who participate in the focus group are not under any obligation to participate in the intervention.

Feasibility and acceptability. We plan to collect multiple sources of information to provide information about feasibility and acceptability:

(1) We will document our challenges and decisions across all aspects of the study (e.g., recruitment, engagement, obstacles to enrollment) to optimize the translation of our findings; (2) We will collect descriptive data on adherence and participant engagement; (3) We will collect and characterize descriptive information on experience, perceived benefits, and satisfaction; (4) We will conduct focus groups with participants, and those who declined to participate, to better understand "what worked" and "what needs work" with respect to the intervention. We will consult with Duke Roybal Center intervention experts for input on our approach. Fidelity to the treatment will be assessed by [name], who does not lead groups, but will review taped sessions to document adherence (e.g., whether content described in treatment manual is presented during sessions).

Mobility testing. Short Physical Performance Battery (SPPB) will assess lower extremity function and mobility. The 6-Minute Walk Test (6MWT) will assess functional exercise capacity. These measures will occur at Baseline and Week 10.

Mechanisms of change. The Behavioral Activation in Depression Scale (BADS) will assess state characteristics of avoidance and activation. This measure will be administered at baseline and week 5. The Barriers to Being Active Quiz will assess perceived barriers to regular movement-oriented activity. These measures will be administered at baseline and post-intervention.

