Stationary behavior. With no validated questionnaire specific to stationary behavior, self-reported sedentary activity will be assessed at baseline/post-assessment, and weekly during the intervention using the Past-Day Adults' Sedentary Time questionnaire (PAST). The PAST assesses multiple domains of sedentary behavior over the past day; it was found to have the highest correlation to device-based activity compared to other questionnaires. The PAST will be administered at baseline, weekly, midpoint, and post

assessment. Device-based tracking. Participants will wear an Actigraph Actilife 6 accelerometer on the right hip for 7 days prior to MOBA participation. This period will represent the pre-intervention control activity condition for each participant. Participants will similarly wear the Actigraph for 1 week post-intervention. The main outcomes of device-based tracking will be percent change in step count per day, with secondary measures including total activity count, and physical activity energy expenditure.

MOBA intervention sessions will occur weekly.

The following questionnaires will also be administered. PHQ-9 will be collected at baseline and week 10, which is post assessment. Physical Activity Readiness will be collected at baseline. The Brief Health Questionnaire will be collected at baseline and week 10. At the final session, a MOBA Class Feedback form will be completed by the participants.

As shown in Table 1, participants will complete a baseline assessment administered by a fitness specialist that includes questionnaires and mobility testing. These assessments will be repeated at end of the intervention. Additionally, the wait-list control group will complete a third assessment at the end of their 02-week participation in MOBA.

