**Table 1. Study assessments**

Aim 1 (pre- and post- intervention)	Acceptability & feasibility: Characterize and document process measures of intervention engagement; descriptive data (e.g., % attendance, % homework completion); participant experience questionnaires, focus groups
Aim 2 (pre- and post- intervention)	Mobility: SPPB, 6MWT, Activity: Actigraph average steps per day, PAST (subjective activity)
Aim 3 (pre- and post- intervention)	Activation/Avoidance: BADS, Barriers: BBAQ
Note: Wait-list control group will be assessed at 3 timepoints: baseline (at waitlist), pre-intervention, post-intervention	

April 6, 2022 An amendment to remove the participant initials from the last page of the consent is incorporated to prevent consent deviations.

May 16, 2022 An amendment to request permission for a magazine article e.g., Work at Duke, to be written about the MOBA project. This article will include pictures of participants and interviews, if they agreed. These pictures would require a release to other purposes, such as presentations or an eventual website. It is hoped that the article could be written with the next set of assessments, which is scheduled near the end of June. By participating in the article, participant's involvement would no longer be confidential.

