## Selection of Subjects

- List inclusion/exclusion criteria and how subjects will be identified.

**Participants.** Inclusion: The pilot cohort will be composed of members of the Duke Dining Service staff age 30-64. The age range was chosen to target the critical window for establishing the long-term geroprotective benefits of increasing movement-oriented behaviors. The age range has also been expanded to allow for participation by all members of the Dining Service. The workplace cohort was chosen because their work demands are characterized by a high level of stationary activity, and because of previous success recruiting this group to participate in the Healthy Duke *Making the Connection* (MTC) wellness initiative. Additionally, 58% of this cohort reported >5 hours sitting per day, which indicates high levels of sedentary behavior in addition to stationary behavior at work. In MTC, the participating cohort was 72% female, and 80% were between age 30-64. Exclusion: 1) individuals with moderate or greater depression severity (PHQ-9 > 14); and 2) individuals with significant mobility limitation, defined as inability to complete 6 Minute-Walk Test. We plan to include rather than exclude individuals with medical comorbidities (e.g., diabetes, cardiac conditions, obesity) because this provides the most representative sample of the stationary population, and is consistent with our goal of developing a cross-cutting and translatable intervention. The Dining Services workforce is >90% African American, which is a group with disproportionately lower physical activity; and 3) individuals who answer "Yes" to any of the questions on the Physical Activity Readiness Questionnaire (PAR-Q) will be encouraged to consult with their physician before proceeding with the study. Physician clearance is not required for participation. Sample size. We plan to recruit 16 individuals for each of the two MOBA groups (N = 32), which allows for 23% attrition based on prior MTC completion rates.

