### Data Analysis & Statistical Considerations

- Describe endpoints and power calculations. Provide a detailed description of how study data will be analyzed, including statistical methods used, and how ineligible subjects will be handled and which subjects will be included for analysis. Include planned sample size justification. Provide estimated time to target accrual and accrual rate. Describe interim analysis including plans to stop accrual during monitoring. Phase I studies, include dose escalation schema and criteria for dose escalation with definition of MTD and DLT.

Sample size was based on previous recommendations from Lancaster et al. that targeting approximately 30 participants is a pragmatic standard for feasibility trials. While we recognize this sample size will not allow us to derive meaningful effect size estimates for between-group comparisons in this pilot study, it will be useful in determining the acceptability of the proposed intervention and deriving variance metrics (e.g., standard deviation of physical activity outcomes) for the purposes of future effect size estimation. We acknowledge that the proposed sample size is not adequate for formally testing group differences or effect size metrics. We will therefore (a) interpret these comparisons as preliminary, (b) characterize effect sizes for pre-to-post changes within each group separately, and (c) characterize group changes in actigraphy using contemporary minimum clinically important difference (MCID) metrics (e.g., 500 steps / day).

**Analysis plan for Aim 1.** We plan to collect multiple sources of information to provide information about feasibility and acceptability: (1) We will document our challenges and decisions across all aspects of the study (e.g., recruitment, engagement, obstacles to enrollment) to optimize the translation of our findings; (2) We will collect descriptive data on adherence and participant engagement; (3) We will collect and characterize descriptive information on experience, perceived benefits, and satisfaction; (4) We will conduct focus groups with participants, and those who declined to participate, to better understand "what worked" and "what needs work" with respect to the intervention. We will consult with Duke Roybal Center intervention experts for input on our approach. Areas of efficacy: We will use data from the PAST questionnaire to identify which domains of activity are most and least responsive to MOBA. Fidelity to the

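### The MOBA Class Feedback form is given only at the final session, so satisfaction measured on that form may be overstated

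*Combined protocol and SAP*

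**What the plan says.** In the protocol's Assessments section the form has a single time of administration: "At the final session, a MOBA Class Feedback form will be completed by the participants". No other section gives it at another time or to anyone not present.

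The analysis plan for Aim 1 (Data Analysis & Statistical Considerations) promises this: "We will collect and characterize descriptive information on experience, perceived benefits, and satisfaction". It names no instrument, denominator or threshold. The Class Feedback form is the only named instrument that fits.

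The same plan has other sources for Aim 1. It says "We will collect descriptive data on adherence and participant engagement", and Table 1 lists "descriptive data (e.g., % attendance, % homework completion); participant experience questionnaires, focus groups". On focus groups, the Assessments section says "We will conduct focus groups with participants, and those who declined to participate". Participant Remuneration budgets a 2-month follow-up interview for 32 people and a non-participant interview for 20, without describing the content of either.

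Selection of Subjects sets enrolment at two groups of 16, "which allows for 23% attrition based on prior MTC completion rates". The Overview has half of the participants wait 10 weeks before they start MOBA.

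**The concern.** Whether a person is asked for an opinion of the class depends on whether that person was still attending at the end. Continued attendance is itself a sign of acceptability, so the form selects its respondents on something close to what it measures. Anyone who started and stopped, or was away that day, gives no rating on it.

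This matters more here than in a trial with a powered efficacy endpoint. Acceptability is part of Aim 1. The statistical section concedes that the sample is too small to test group differences and justifies it partly by what it will show about acceptability. A pilot is also where reasons for stopping are most useful, because the intervention can still be revised. The plan takes care to reach people who declined, but nowhere names those who began and left as a group to be approached.

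**Working it through.** **Inputs from the documents.** Enrolment is 2 × 16 = 32, which reproduces the stated N. Attrition is 23%, taken from completion rates in an earlier workplace wellness programme (Selection of Subjects). The form is given at the final session only (Assessments).

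**Expected numbers.**
- Completers: 32 × 0.77 = 24.6, or 16 × 0.77 = 12.3 per group.
- Lost: 32 × 0.23 = 7.4, so about 7 to 8 people.

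**Formula.** Let q be the favourable share among those who complete the form, r the share among those not asked, and m the share not asked. The form reports q. The figure for everyone is (1 − m)q + m·r. The difference is q − [(1 − m)q + m·r] = m(q − r).

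The documents give neither q nor r, so every value of them below is an assumption.

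**Results at m = 0.23.**
- r = q: 0.23 × 0 = 0 points.
- q = 90%, r = 50%: 0.23 × 40 = 9.2 points.
- q = 100%, r = 0%: 0.23 × 100 = 23 points, the largest possible value.

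**The same in whole people.** Suppose 25 complete the form, 22 of them favourably (22/25 = 88%), and 7 are not asked.

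| Favourable among the 7 (assumed) | All 32 | Form minus all 32 |
|---|---|---|
| 75% | (22 + 5.25)/32 = 85.2% | 2.8 points |
| 50% | (22 + 3.5)/32 = 79.7% | 8.3 points |
| 25% | (22 + 1.75)/32 = 74.2% | 13.8 points |
| 0% | 22/32 = 68.8% | 19.2 points |

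If all 7 were favourable, the figure would be 29/32 = 90.6% and the form would understate by 2.6 points. The direction is therefore plausible but not fixed.

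**Allowing for the waitlist.** People lost before any session have no class to rate and do not belong in the denominator. Suppose the whole expected loss in the waitlist group, 16 × 0.23 = 3.68, happened during the wait. The starters would then be 32 − 3.68 = 28.32, of whom 3.68 stopped, so m = 3.68/28.32 = 13%. The case q = 90%, r = 50% falls to 0.13 × 40 = 5.2 points, and the largest possible value falls to 13 points.

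**Allowing for absence.** Each person still enrolled but away on the last day adds 1/32 = 3.1 percentage points to m. The 23-point limit applies to the planned attrition without such absences.

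**The case against.** The strongest reply is that this form is not the whole of Aim 1. The protocol calls it class feedback, does not make it the acceptability endpoint, and says that several sources will be used. Attendance and homework completion record disengagement directly, including in people who leave. The focus groups are for participants, a word that can include someone who started and stopped. The 2-month interview is budgeted for 32, the full planned enrolment with no deduction for attrition. A form at the end of a class is also an ordinary choice in a small descriptive pilot.

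Much of this stands. A reader might infer that people who stop are never asked anything, or that Aim 1 acceptability as a whole will be overstated. The documents support neither. The interview and focus groups may reach those people, and other sources do not depend on the form. A certain upward bias is not shown either: no section says why people leave or how they would rate MOBA, and some may leave for reasons unrelated to the class. It is also right that 23% comes from another programme and covers all enrolled, so about 7 of 32 is only an approximate planning figure for starters who stop.

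What does not fall is the narrower point. Attendance shows that someone left, not what they thought or why. The interview appears only as a payment line, with no stated content, link to Aim 1 or invitation to people who stopped. None of these sources is stated to collect the form's items from them.

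**Conclusion.** The point holds for the form. Followed as written, the plan yields a satisfaction summary restricted to those present at the final session, and that summary may be too favourable. About 7 of 32 could be missed at the planned attrition, fewer if some losses fall on the waitlist and more with absences on the day. The bias lies between zero and about 23 points upward, provided that those missed are no more favourable than those asked and that attrition is as planned; its actual size cannot be known from the documents. The other Aim 1 sources reduce the consequence but do not close the gap. This is a worthwhile, inexpensive improvement to one Aim 1 measure; it does not invalidate the aim.

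**What to change.** In the Assessments section, offer the Class Feedback form to everyone who attended at least one MOBA session. Attendees complete it at the final session. Others receive it at the post-intervention assessment, which is already paid for, or by phone or email. For the waitlist group this means the assessment after their own MOBA course. Add one item on the reason for stopping.

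In the analysis plan for Aim 1, report the form's results with the number who started, the number who responded and the number not reached, next to attendance. State that people who started and stopped will be invited to the focus groups and to the 2-month interview.

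The cost is a wording amendment, one extra item and contact with about 7 to 8 people plus anyone absent from the last session. The satisfaction figures may come out less favourable. No change to the sample or the intervention is needed.

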**Table 1. Study assessments**

Aim 1 (pre- and post- intervention)	Acceptability & feasibility: Characterize and document process measures of intervention engagement; descriptive data (e.g., % attendance, % homework completion); participant experience questionnaires, focus groups
Aim 2 (pre- and post- intervention)	Mobility: SPPB, 6MWT, Activity: Actigraph average steps per day, PAST (subjective activity)
Aim 3 (pre- and post- intervention)	Activation/Avoidance: BADS, Barriers: BBAQ
Note: Wait-list control group will be assessed at 3 timepoints: baseline (at waitlist), pre-intervention, post-intervention	

April 6, 2022 An amendment to remove the participant initials from the last page of the consent is incorporated to prevent consent deviations.

May 16, 2022 An amendment to request permission for a magazine article e.g., Work at Duke, to be written about the MOBA project. This article will include pictures of participants and interviews, if they agreed. These pictures would require a release to other purposes, such as presentations or an eventual website. It is hoped that the article could be written with the next set of assessments, which is scheduled near the end of June. By participating in the article, participant's involvement would no longer be confidential.

## Selection of Subjects

- List inclusion/exclusion criteria and how subjects will be identified.

**Participants.** Inclusion: The pilot cohort will be composed of members of the Duke Dining Service staff age 30-64. The age range was chosen to target the critical window for establishing the long-term geroprotective benefits of increasing movement-oriented behaviors. The age range has also been expanded to allow for participation by all members of the Dining Service. The workplace cohort was chosen because their work demands are characterized by a high level of stationary activity, and because of previous success recruiting this group to participate in the Healthy Duke *Making the Connection* (MTC) wellness initiative. Additionally, 58% of this cohort reported >5 hours sitting per day, which indicates high levels of sedentary behavior in addition to stationary behavior at work. In MTC, the participating cohort was 72% female, and 80% were between age 30-64. Exclusion: 1) individuals with moderate or greater depression severity (PHQ-9 > 14); and 2) individuals with significant mobility limitation, defined as inability to complete 6 Minute-Walk Test. We plan to include rather than exclude individuals with medical comorbidities (e.g., diabetes, cardiac conditions, obesity) because this provides the most representative sample of the stationary population, and is consistent with our goal of developing a cross-cutting and translatable intervention. The Dining Services workforce is >90% African American, which is a group with disproportionately lower physical activity; and 3) individuals who answer "Yes" to any of the questions on the Physical Activity Readiness Questionnaire (PAR-Q) will be encouraged to consult with their physician before proceeding with the study. Physician clearance is not required for participation. Sample size. We plan to recruit 16 individuals for each of the two MOBA groups (N = 32), which allows for 23% attrition based on prior MTC completion rates.

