Official Title: Movement-Oriented Behavioral Activation (MOBA) to Reduce Stationary Behavior

DUHS IRB Application Version 1.13

Pro00108020

Approval Date: 09/09/2022

NCT04892147

**Aim 1:** Determine feasibility and acceptability of a 10-week group MOBA intervention for individuals with excessive stationary behavior compared to waitlist control.

**Aim 2:** Assess activity and mobility changes following a 10-week group MOBA intervention for individuals with excessive stationary behavior compared to waitlist control.

**Hypothesis:** Individuals completing MOBA will have greater (1) improvement in physical performance, (2) reduction in sedentary time, and (3) increase in daily step count after 12 weeks compared to the control group.

**Aim 3:** Examine changes in activation, avoidance, and perceived barriers to physical activity after a 12-week group MOBA intervention for individuals with excessive stationary behavior compared to waitlist control.

**Hypothesis:** Individuals completing MOBA will have greater (1) increase in activation, (2) decrease in avoidance, and (3) decrease in self-reported barriers to physical activity after 12 weeks compared to the control group.

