#### Overview.

The study uses randomized waitlist-control design. We propose to randomly assign half of participants to (a) 10 weeks of MOBA intervention, and half of participants to (b) a 10-week waitlist, followed by 10 weeks of MOBA.

**Intervention.** MOBA is adapted from established protocols to integrate traditional behavioral activation (BA) principles with strategies to incorporate values-based, goal-directed movement into daily routines. The BA content of MOBA is adapted from co-investigator [name] intervention Behavioral Activation Therapy for Anhedonia (BATA). MOBA reduces depression-related content relative to BATA and increases focus on values that engage individuals in movement-related activity. MOBA is designed as a group intervention to leverage the reward value of social contact, and the positive influence of group problem-solving and accountability on behavior change. MOBA preserves the principles and general sequence of sessions used in BATA, but incorporates movement-oriented content: (a) provide psychoeducation about risks of physical inactivity, behavioral barriers to activity, and rationale for the treatment approach; (b) explore personal values, non-stationary, movement-oriented activities that support those values, and a hierarchical plan for goal attainment; (c) identify and assign weekly activities related to the valued goals; (d) address common barriers to engagement with valued activities including avoidance, low behavioral initiation, and an overemphasis on felt motivation as a prerequisite for action; and (e) monitor, support, and reward achieving behavioral goals. Content unique to MOBA includes: 1) demonstration and participation in physical activities that provide alternatives to stationary behavior, including select activities used in a previous study with the Dining Services cohort (e.g., stairs, body-weight squats, knee raises), and 2) generation of person-centered strategies for integrating movement-oriented activities into daily routines across the three domains of the Behavior Settings Model: 1) workplace sitting/prolonged standing, 2) screen-focused home activities, 3) time spent sitting in automobiles. Weeks 1-4 address topics a-c; weeks 5-12 address topics d-e. MOBA will be facilitated by a clinician ([name]) and a wellness educator ([name]), who will be trained on the MOBA treatment manual. The facilitators' role is to provide teaching, support, encouragement, and guidance throughout the intervention. Weekly sessions will take place in a dedicated conference room near the workplace, during the last hour of the workday (4-5 pm), and is counted as paid time at work.

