#### **Participant Remuneration**

Baseline assessment (\$50), post-intervention assessment (\$70), 2-month follow-up interview (32 x \$20), non-participant interview (20 x \$20).

We plan assessment proximate to the workplace, so there will be no travel costs. The intervention occurs on paid time, and will not result in lost wages.

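### With 23% attrition allowed for, does the plan need to state who is analysed and how people without post data are handled?

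*Combined protocol and SAP*

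**What the plan says.** Selection of Subjects plans 16 people in each of two groups, "which allows for 23% attrition based on prior MTC completion rates". The Overview randomises half to immediate MOBA and half to "a 10-week waitlist, followed by 10 weeks of MOBA".

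The institutional prompt at the head of Data Analysis & Statistical Considerations asks "how ineligible subjects will be handled and which subjects will be included for analysis". The text beneath it gives a rule-of-thumb basis of about 30 participants and concedes that this is too few for formal group testing. It calls between-group comparisons preliminary and relies on within-group effect sizes, a descriptive reading against 500 steps/day, and SDs for later planning. The analysis plans for Aims 2 and 3 list baseline-to-post mean differences, percent change and effect size. None of this text names an analysis set or a missing-data rule.

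The only wording on who is compared is in the opening hypotheses. Aim 2 has "Individuals completing MOBA will have greater (1) improvement in physical performance, (2) reduction in sedentary time, and (3) increase in daily step count" and Aim 3 has "Individuals completing MOBA will have greater (1) increase in activation", each against the control group. Completion is not defined.

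Other text leans towards following everyone. Of the baseline battery, Assessments says "These assessments will be repeated at end of the intervention", without an attendance condition. Participant Remuneration budgets the "2-month follow-up interview" for 32 people.

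**The concern.** The plan expects to lose nearly a quarter of its participants, is asked who will be analysed, and does not answer. The one hint, in the hypotheses, points to completers.

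At week 10 the waitlist arm has had no sessions to complete. A completer filter on the randomised contrast would therefore remove people from the MOBA arm alone, because of something that happened after randomisation. If those who stay tend to improve more for reasons unrelated to MOBA, a difference could appear with no effect of the intervention. The within-group effect sizes, the 500 steps/day reading and the SDs also depend on who is counted, and the plan offers these in place of formal testing.

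**Working it through.** **The plan's own figures.** 2 × 16 = 32. With 23% attrition, 32 × 0.23 = 7.4 are lost and 32 × 0.77 = 24.6 remain. Per group this is 16 × 0.77 = 12.3 remaining and 16 × 0.23 = 3.7 lost. No alpha, power, effect size or SD is given, so there is no power calculation to reproduce. Thirty people retained would need 30 / 0.77 = 39 recruited, so the rule-of-thumb 30 fits the number recruited. Twelve retained per group gives 12 / 0.77 = 15.6, rounded up to 16, but the plan never states 12. Naming an analysis set changes none of these numbers.

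**What each reading does at week 10.**
- One-arm filter (hypothesis wording applied literally, no waitlist loss): about 12 MOBA v up to 16 waitlist.
- Loss in both arms (23% taken as missed assessments): about 12 v 12.
- Everyone assessed: 16 v 16.

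**Sampling error.** The 95% half-width in SD units is t × √(1/n₁ + 1/n₂).
- 12 v 16: 2.056 × 0.382 = 0.785
- 12 v 12: 2.074 × 0.408 = 0.847
- 16 v 16: 2.042 × 0.354 = 0.722
- Within one arm, n = 12: 2.201 / √12 = 0.635

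**Bias from a one-arm filter with no true effect.** The documents give no outcomes for people lost, so this rests on an assumption. Let staying depend on a normal score that correlates ρ with change, with the top 77% staying. The cut is z = −0.739, φ(z) = 0.304, and the shift is ρ × φ(z) / 0.77 = ρ × 0.394.

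| Assumed ρ | Shift (SD) | Share of 0.785 | Share of 0.635 (within arm) |
|---|---|---|---|
| 0.1 | 0.039 | 5% | 6% |
| 0.3 | 0.118 | 15% | 19% |
| 0.5 | 0.197 | 25% | 31% |

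Simulation (16 v 16 randomised, 40,000 runs per ρ) gives 0.035, 0.119 and 0.196 when only the MOBA arm is filtered. When both arms lose people by the same process, the difference is within 0.01 of zero.

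**SDs for later planning.** With λ = 0.394, the variance of change among those who stay is 1 − ρ² × λ(λ − z) = 1 − ρ² × 0.394 × 1.133 = 1 − 0.447ρ². At ρ = 0.5 this is 0.888, an SD ratio of 0.94. At ρ = 0.3 it is 0.960, a ratio of 0.98. The relative standard error of an SD from 12 people is about 1/√(2 × 11) = 0.21, so the 2% to 6% shrinkage is well inside it.

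**Which reading the text supports.** A baseline-to-post difference can be computed only for someone with both measurements. The default set is therefore everyone with post data, in the group assigned. The schedule asks for that measurement whether or not sessions were attended. Nothing in the analysis section drops an assessed person for poor attendance. The note to Table 1 gives the waitlist arm a pre-intervention assessment, which supplies its week-10 value. For step counts, the device paragraph sets wear before and after MOBA, and of the pre-MOBA week it says "This period will represent the pre-intervention control activity condition for each participant". On that wording even a completer filter on step change could act on both arms, since both eventually receive MOBA.

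**The case for a change.** The strongest case for a change is that the remedy is cheap. The prompt asks a direct question, two or three sentences would answer it, and the only wording a reader could fall back on names completers. Calling the study a pilot does not dispose of this, because the within-group effect sizes and SDs it offers instead of tests also depend on who is counted. Feasibility is Aim 1, so numbers randomised and assessed by arm are basic results.

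Much of this is right. The silence is real, and no other section fills it. Stating the set, and putting assigned in place of completing in the hypotheses, would be tidier.

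It still does not show that the plan as written leads to a wrong result. A hypothesis sentence is not an analysis set, and the one-arm reading also needs virtually no loss from the waitlist, whereas the 23% is allowed for across both groups. An explicit rule to analyse everyone with post data, regardless of attendance, would restate what the planned differences and the assessment schedule already imply. It would not recover those who never return for the post assessment. Aim 1 already commits to descriptive data on adherence and engagement, including attendance and homework percentages, so loss will be visible in the report.

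**Conclusion.** The concern identifies missing detail, not an error that would alter the pilot's conclusions. About 7 of 32 people may lack post data. The natural analysis uses the remaining 25 or so in their assigned groups, and a competent analyst would do this and report the counts by arm.

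The damaging version needs three things the documents do not establish: that the hypothesis wording governs the analysis, that loss falls only on the MOBA arm, and that staying is related to change. Granting all three, the false difference is 0.04 to 0.20 SD for assumed correlations of 0.1 to 0.5, at most a quarter of one 95% half-width, in a comparison the plan already calls preliminary. With the same loss process in both arms it is about zero. The 500 steps/day figure is an example benchmark with no decision attached.

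No change to the plan follows on this point. The hypotheses refer to 12 weeks while the Overview and Assessments use week 10. Those passages must be reconciled, but that is a separate matter and does not affect this conclusion.
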